## Statistical Analysis Plan

The **primary outcome** is the post-dose difference in breathlessness intensity ratings during exercise at isotime, defined as the highest equivalent 1-minute interval of exercise completed by a given participant during each constant-load CPET. The **co-primary outcome** is the post-dose difference in exercise endurance time (EET), defined as the duration of loaded pedaling during constant-load CPET. Secondary outcomes include additional physiological and perceptual responses assessed at isotime and at peak exercise (end of test).

### Data Presentation:

- Normally distributed continuous variables will be expressed as mean  $\pm$  standard deviation (SD).
- Skewed continuous variables will be expressed as median with range or interquartile range (IQR).
- Categorical variables will be presented as frequencies and percentages.

### Comparisons:

- Baseline characteristics will be compared using independent t-tests (continuous normal), Wilcoxon rank-sum tests (continuous non-normal), and chi-square tests (categorical).
- For CPET outcomes, within-subject comparisons between menthol and placebo will be performed using paired t-tests for normally distributed variables and Wilcoxon signed-rank tests for non-normal variables. Categorical outcomes will be analyzed using McNemar's test.
- CPET variables will be compared between conditions at isotime and peak exertion.

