### Modeling:

Changes during CPET may be further analyzed using mixed-effects regression models to account for repeated measures.

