### Reporting:

Estimates will be presented as mean differences (menthol minus placebo) with 95% confidence intervals (CIs). Statistical significance will be defined as two-sided  $p < 0.05$ .

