**Figure 1: CONSORT diagram showing the flow of participants through each stage of the study**

**Table 1: Baseline participant characteristics ( t-test for continuous variables with normal distribution, ranksum test for continuous non-normal variables and chi-square for categorical variables).**

Parameter	Menthol first	Placebo first	All participants
N (%)			
Male:female (n)			
Age, mean years (SD)			
Height (cm)			
Weight (kg)			
BMI kg/m  , mean (SD)			
Smoking history, pack-years (SD)			
Physical activity during normal week			
Post-bronchodilator pulmonary function (spirometry)			
FEV 1 , L (SD)			
FEV 1 , % predicted (SD)			
FVC, L (SD)			
FVC, % predicted (SD)			
FEV 1 /FVC, L (SD)			
FEV 1 /FVC, % of predicted (SD)			
Breathlessness and health status			
mMRC 0-4			
CAT total Score			
CAT breathlessness			
CAT activity limitation			
MDP A1 total			
Dyspnea 12			
Dyspnea severity likert			
SF12 q1 – q12			
Change between visit 1 and 2 (GIC-scale)			
Change between visit 2 and 3 (GIC-scale)			
Underlying conditions			
Ischaemic heart disease			
Angina Pectoris			
AF			
Heart failure			
Hypertension			
Hyperlipidemia			
Diabetes			

Obstructive sleep apnea			
Asthma			
Other lung disease			
Tuberculosis			
Rheumatic disease			
Stroke			
Cancer			
Depression or anxiety			
None			
Other			
Medications			
Diuretics			
Beta blocker			
Calcium antagonist			
Renin-angiotensin system blocker			
Insulin			
Other diabetic medication			
Anti hyperlipidemic drug			
Inhalators for COPD/asthma			
Anticoagulants			
Antidepressants/anxiolytics			
Sleep medication or other benzodiazepines			
Other			
COPD medication			
LABA+LAMA			
LABA+LAMA+ICS			
LABA			
LAMA			
LABA+LAMA+Daxas			
LABA+LAMA+ICS+Daxas			
Physiological responses at incremental cycle test (visit 1)			
Cycle exercise time (min)			
Workload, W			
Workload, % of predicted			
Heart rate, beats/min			
Breathing frequency (breaths/min)			
SpO 2 (%)			
V O2 , mL/kg/min,			
V O2 (% of predicted),			
V'CO 2 (ml/kg/min)			

RER			
$V'_{E, L/min}$			
$V_T, L$			
$V'_E/V'_{CO_2}$			
Perceptual responses during test (visit 1)			
Breathlessness intensity, Borg units			
Breathlessness discomfort, Borg units			
Leg discomfort, Borg units			
Reasons for stopping exercise (visit 1)			
Breathlessness (n)			
Leg discomfort (n)			

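### The tests for both primary outcomes ignore treatment order and visit in a two-order, two-visit crossover

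*SAP*

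**What the plan says.** The SAP's opening section names two primary outcomes: the "post-dose difference in breathlessness intensity ratings during exercise at isotime" and the corresponding difference in exercise endurance time. The Comparisons section fixes the test for all exercise-test outcomes, these two included: "within-subject comparisons between menthol and placebo will be performed using paired t-tests", with Wilcoxon signed-rank tests where a variable is not normal. The Reporting section then promises a menthol-minus-placebo mean difference with a 95% confidence interval.

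The design can be read from the table shells. Table 1 has columns for "Menthol first" and "Placebo first", and Table 2 draws its data from Visits 2 and 3. The order columns serve only the baseline table. Table 1 also lists a global impression of change between Visits 2 and 3, but no treatment comparison uses it.

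The only model in the plan is in the Modeling section: "Changes during CPET may be further analyzed using mixed-effects regression models to account for repeated measures". It is optional, concerns the course within an exercise test, and names neither a period nor a sequence term.

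**The concern.** In a crossover with two orders, treatment and visit are separated only by comparing the two orders. A paired test pools everyone's menthol-minus-placebo difference and discards the order. Any general change from Visit 2 to Visit 3, such as familiarity with the test, then enters the differences with opposite signs in the two orders.

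With equal orders the shift cancels in the mean but still inflates the variance that the test uses. With unequal orders it does not cancel. For example, if endurance time lengthens at the second treatment visit and more completers took placebo first, menthol is flattered. The estimate, interval and test of both primary outcomes are affected.

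The SAP neither states nor predicts such a shift. One is plausible with repeated exercise tests, and nothing in the stated analysis would handle it.

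**Working it through.** **Inputs.** From the SAP: two orders, Visits 2 and 3, paired tests, two-sided 5% level. The SAP gives no sample size, SD, effect, order split or shift, so there is no planned figure to reproduce. Assumed for illustration: N = 20, normal errors, within-order SD of the menthol-minus-placebo difference set to 1, true effect τ = 0.66 (80% power), and shift π (Visit 3 minus Visit 2) of 0 to 1.0.

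**Bias.** Let D be menthol minus placebo.
- Menthol first: E(D) = τ − π.
- Placebo first: E(D) = τ + π.
- The paired mean therefore estimates τ + π × (n_placebo-first − n_menthol-first)/N.
- The average of the two order-specific means is [(τ − π) + (τ + π)]/2 = τ, whatever the split.

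**Variance.** With a share p in one order, the sample variance of D has expectation 1 + 4p(1 − p)π² × N/(N − 1). At 10/10 this is 1 + π² × 20/19, although the true variance of the mean is still 1/N. The interval is therefore widened by √(1 + π² × 20/19), which is 1.005, 1.032, 1.124 and 1.433 for shifts of 0.1, 0.25, 0.5 and 1.0. Multiplied by the no-shift half-width of 0.462, this gives 0.464, 0.477, 0.519 and 0.662, which agrees with the simulation below.

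**Equal orders (10/10), paired t-test, 100,000 runs per cell**

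| Shift (SD) | Power | Type I error | CI half-width (SD) |
|---|---|---|---|
| 0 | 0.801 | 4.9% | 0.462 |
| 0.1 | 0.797 | 4.8% | 0.464 |
| 0.25 | 0.779 | 4.4% | 0.477 |
| 0.5 | 0.723 | 3.0% | 0.519 |
| 1.0 | 0.493 | 0.6% | 0.664 |

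The order-adjusted analysis (average of the two order means, pooled variance, N − 2 degrees of freedom) has power 0.796–0.798, type I error 4.9–5.1% and half-width 0.463–0.464 throughout.

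**Unequal orders, shift 0.5 SD.** The larger group is taken as placebo first; the sign reverses otherwise.

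| Split | Bias | Paired type I error |
|---|---|---|
| 11/9 | 0.5 × 2/20 = 0.05 SD | 3.3% |
| 12/8 | 0.5 × 4/20 = 0.10 SD | 4.5% |
| 13/7 | 0.5 × 6/20 = 0.15 SD | 6.6% |
| 20/10 (N = 30) | 0.5 × 10/30 = 0.167 SD | 10% |

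The adjusted analysis shows no bias and about 5% in each. Mild imbalance does not raise type I error, because the inflated variance offsets the bias, but the estimate is biased at every unequal split.

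**Non-normal branch.** Let Z be Visit 3 minus Visit 2. Its expectation is π + τ for placebo first and π − τ for menthol first, so the difference between orders is 2τ and π drops out. A rank-sum test of Z between orders therefore adjusts for the visit. At 10/10, for shifts of 0.1, 0.25, 0.5 and 1.0 SD, the signed-rank test has power 0.774, 0.758, 0.695 and 0.436, against 0.749–0.755 for the rank-sum test (40,000 runs). At 13/7 with a 0.5 SD shift, type I error is 6.4% against 4.4%.

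**The case against.** Four objections carry weight.

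- **The harm depends on unseen inputs.** At shifts of 0.1 to 0.25 SD with equal orders the loss is trivial and on the conservative side. This stands, and it limits how strongly the point can be pressed.
- **The bias is conditional on the realised split.** If orders are assigned 1:1 at random (an assumption), the expected imbalance is zero. With simple 1:1 assignment of 20 participants, paired type I error was 5.0%, 4.9% and 5.1% at shifts of 0.25, 0.5 and 1.0 SD, with bias about zero. The test is then valid on average. It still has power of only 0.78, 0.71 and 0.50, and the trial reports one estimate from the split it actually obtains, which drop-out can also unbalance.
- **For small shifts adjustment gains little or nothing.** Root mean square error is √(1/N + bias²) for the paired mean and ½√(1/n₁ + 1/n₂) for the adjusted one. At 12/8 the adjusted value is ½√(1/12 + 1/8) = 0.228. The paired value is √(0.05 + 0.02²) = 0.224 at a shift of 0.1 SD and √(0.05 + 0.05²) = 0.229 at 0.25 SD. At 0.5 SD it is √(0.05 + 0.10²) = 0.245, so the adjusted estimate is then clearly better.
- **The rank-based replacement is weaker at small shifts.** It has less power than the signed-rank test at shifts up to 0.1 SD and is about level at 0.25 SD. The powers above assume normal errors, which is not the case this branch is meant for. In further simulation with heavy-tailed and lognormal errors, however, the rank-sum test held its level and its power. Half a Hodges–Lehmann shift is also not a mean difference, so the Reporting section would need to say so.

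Paired tests are a recognised analysis, and no SAP statement on this point is false. The point is that the stated analysis leaves out a design factor the trial already records.

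**Conclusion.** The concern holds. The analysis fixed for both primary outcomes uses neither order nor visit, and the optional model does not supply them. The bias formula and the variance inflation follow from the design alone. Their size does not: it depends on a shift, an SD and an order split that the SAP does not give.

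Under the illustrative N = 20, a 0.5 SD shift costs about 0.07 to 0.08 of power with equal orders (0.723 against 0.796–0.798). It biases the estimate by 0.05 to 0.15 SD at splits from 11/9 to 13/7, and of those splits only 13/7 takes type I error above 5%. Shifts below about 0.25 SD with near-equal orders matter little. The change is worth making because it is cheap and removes the dependence on the shift. The paired tests are not invalid in general.

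**What to change.** - **Primary analysis of both outcomes.** Use a linear mixed model with fixed effects for treatment, period (Visit 2 or 3) and sequence, and a random participant effect. Report its menthol-minus-placebo estimate and 95% confidence interval. With complete pairs the estimate is the average of the two order-specific mean differences. In one simulated 12/8 data set both were −0.698, against −0.605 for the plain paired mean.
- **Non-normal branch.** Replace the signed-rank test by a rank-sum test of the Visit 3 minus Visit 2 differences between the orders. Report half the Hodges–Lehmann shift (placebo first minus menthol first) with its 95% interval, and state under Reporting that this is a location shift and not a mean difference.
- **Sensitivity analyses.** Keep the unadjusted paired t-test and signed-rank test.

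**Cost.** SAP wording, one model command and, for the rank branch, one further procedure; no extra data. If there is no shift, power changes as follows.

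| Split | Paired t → adjusted | Signed-rank → rank-sum |
|---|---|---|
| 10/10 | 0.801 → 0.798 | 0.78 → 0.75 |
| 12/8 | 0.80 → 0.78 | 0.78 → 0.75 |
| 13/7 | 0.80 → 0.76 | 0.78 → 0.72 |

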Breathlessness and Leg discomfort (n)			
Breathlessness ratings after test (visit 1)			
MDP (A1 + dimensions)			
D12			
Self-reported motivation for completing test (visit 1)			

**Table 2:** Effect of menthol versus placebo on physiological and perceptual responses at a standardized submaximal time during constant-load exercise testing (isotime) and at the symptom limited peak of constant-load exercise testing among individuals with Chronic obstructive pulmonary disease. (t-test for continuous variables with normal distribution, ranksum test for continuous non-normal variables and chi-square for categorical variables). **(Visit 2 and 3)**

Parameter, mean (SD)	Rest			Isotime			Peak		
	Menthol	Placebo	Mean difference (95% CI)	Menthol	Placebo	Mean difference (95% CI)	Menthol	Placebo	Mean difference (95% CI)
Physiological responses									
Cycle exercise time, min									
Heart rate, beats/min									
Breathing frequency, breaths/min									
SpO 2 , %									
V' O2 , ml/kg/min									
V' O2 , % of predicted									
V' CO2 (ml/kg/min)									
RER									
V' E , L/min									
V T , L									
V' E /V' CO2									
PETH CO 2									
Perceptual responses									
Breathlessness intensity (Borg CR10)									
Breathlessness unpleasantness (Borg CR10)									
Leg discomfort (Borg CR10)									
Significant breathlessness (>2, n (%))									
Reasons for stopping test									
Breathlessness (n)									
Leg discomfort (n)									

Breathlessness and Leg discomfort (n)								
Level of self-reported motivation								
Breathlessness ratings after tests								
MDP								
Dyspnea 12								

Mean differences are for menthol minus placebo.

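### McNemar's test is assigned to all categorical exercise outcomes, but stopping reason is tabulated in three rows and the Table 2 caption names an unpaired chi-square test for the same rows

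*SAP*

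**What the plan says.** The Comparisons section of the SAP sets the within-participant tests for the exercise outcomes. Continuous variables get paired t-tests, or "Wilcoxon signed-rank tests for non-normal variables". For the rest: "Categorical outcomes will be analyzed using McNemar's test". No extension to more than two categories is named, no collapsing rule is given, and the exact or asymptotic version is not specified.

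Table 2 has a block headed "Reasons for stopping test" with three count rows: breathlessness, leg discomfort, and the two together. Its caption assigns different tests to the same table: a t-test not described as paired, then "ranksum test for continuous non-normal variables and chi-square for categorical variables".

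Under Reporting: "Statistical significance will be defined as two-sided" p < 0.05. No rule covers several linked rows of one item.

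**The concern.** There are two faults.

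1. **The test does not fit the outcome as tabulated.** McNemar's test compares two paired proportions. A three-category item must first be made binary, and the SAP does not say how. The obvious way is to test each row as yes/no. On the exclusive reading of the rows, someone who stops for both reasons is a 'no' in the breathlessness row. A move from breathlessness alone on placebo to both on menthol then counts towards a fall in that row, although breathlessness still limited the test.
2. **The SAP contradicts itself.** The Comparisons section treats the categorical data as paired, while the Table 2 caption names a test for independent groups on the same rows. Neither gives a usable analysis of stopping reason as it stands.

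At stake is how one Table 2 item is read. A significant fall in the breathlessness row could be taken to mean that breathlessness limited fewer tests. An undefined grouping also leaves the choice open until the data are seen.

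**Working it through.** **Inputs.** From the SAP: McNemar for categorical outcomes (Comparisons), three stopping-reason rows and chi-square in the caption (Table 2), and two-sided 0.05 (Reporting). The SAP gives no sample size and no stopping rates, so there is no stated figure to reproduce. All counts below are assumptions chosen to show the mechanism.

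**Step 1: movers needed for a significant breathlessness row.** Let k participants move from breathlessness (placebo) to both (menthol), with no other moves. The breathlessness row then has k discordant pairs, all in one direction, and exact two-sided p = 2 × 0.5^k.

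- k = 5: 2 × 0.5^5 = 0.0625
- k = 6: 2 × 0.5^6 = 0.031
- k = 8: 2 × 0.5^8 = 0.0078

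With 8 moves one way and 1 back, p = 2 × (1 + 9)/2^9 = 0.039.

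The unspecified version matters. The asymptotic statistic is k²/k = k, so k = 4 gives chi-square 4, p = 0.046. With continuity correction it is (k − 1)²/k, so k = 5 gives 3.2, p = 0.074, and k = 6 gives 4.17, p = 0.041.

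**Step 2: one assumed table, N = 20** (rows placebo, columns menthol).

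| | Breathlessness | Leg | Both | Total |
|---|---|---|---|---|
| Breathlessness | 6 | 0 | 8 | 14 |
| Leg | 0 | 4 | 0 | 4 |
| Both | 0 | 0 | 2 | 2 |
| Total | 6 | 4 | 10 | 20 |

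- Breathlessness row: 14 on placebo, 6 on menthol; 8 v 0 discordant; exact p = 0.0078.
- Row for both: 2 on placebo, 10 on menthol; 0 v 8 discordant; exact p = 0.0078, the mirror image.
- Breathlessness alone or combined: 14 + 2 = 16 on placebo, 6 + 10 = 16 on menthol; no discordant pairs; p = 1.0.
- Caption's chi-square on the totals (14, 4, 2) and (6, 4, 10), with expected counts 10, 4 and 6: 2 × 16/10 + 0 + 2 × 16/6 = 8.53 on 2 df, p = exp(−8.53/2) = 0.014. This treats 20 people measured twice as 40 independent observations.

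The same data therefore give 0.0078, 0.014 or 1.0, depending on which instruction and which grouping are followed.

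**Step 3: joint tests of the three categories.** Bowker's statistic is (8 − 0)²/8 = 8.0, with p = 0.046 on 3 df, or 0.0047 on 1 df if only the non-empty pair counts. It tests symmetry, not equality of the margins. For Stuart-Maxwell, drop the category for both. The variance terms are 14 + 6 − 2 × 6 = 8 for breathlessness and 4 + 4 − 2 × 4 = 0 for leg, with covariance 0, so the matrix is singular and the asymptotic statistic cannot be computed. In a sparse table a joint test needs one named method, in exact form.

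**Step 4: how often the pattern would reach p < 0.05.** If each participant makes this move with probability π and nobody moves otherwise, the chance is P(X ≥ 6) with X ~ Binomial(N, π).

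| π | N = 16 | N = 20 | N = 30 |
|---|---|---|---|
| 0.1 | 0.3% | 1% | 7% |
| 0.2 | 8% | 20% | 57% |
| 0.3 | 34% | 58% | 92% |
| 0.4 | 67% | 87% | 99% |

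The chance is small if few move and large if many do. The SAP gives no basis for choosing π or N.

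**The case against.** The strongest reply is that the problem rests on two things the SAP does not state.

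- **Exclusive rows.** If the breathlessness row counts everyone who named breathlessness, and the third row is the overlap, McNemar on the first row is already the sensible analysis and the artefact disappears. This is possible, and the protocol, not shown here, may define the recording. A separate combined row fits exclusive categories better, but that is an inference.
- **Row-by-row testing.** The SAP does not prescribe it. Table 2 has comparison columns for a mean difference with 95% CI and no p-value column. The adjacent row would show the matching rise, and on exclusive coding the fall in breathlessness alone is genuine; the error lies in how the row is read. This stands, so the harm is conditional.

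The worked pattern is also extreme, with all moves in one direction. That stands too.

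A reader might further infer that "Level of self-reported motivation" in Table 2 is wrongly sent to McNemar. The SAP does not class motivation as categorical, and a graded score can fall under the signed-rank rule in the same section.

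What the reply does not remove is the missing rule for a three-row item and the conflict between the Comparisons section and the caption. Both are visible in the text under either reading of the rows.

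**Conclusion.** The point holds as a minor one. Two parts need no assumption: the SAP assigns a test for paired binary data to an item tabulated in three rows without saying how to reduce it, and the Table 2 caption names an unpaired test for the same rows.

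The misleading result is conditional on exclusive rows, separate row tests and moves that run mainly from breathlessness to both. Under those assumptions six one-way moves suffice on the exact test (p = 0.031) and five do not (p = 0.0625).

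A reader might infer that the trial's main conclusions are at risk, or that a false fall in stopping for breathlessness will be reported. The SAP supports neither. The primary outcome (breathlessness intensity at isotime) and co-primary outcome (exercise endurance time) do not use McNemar's test, stopping reason is not named among the outcomes in the opening section, and nothing there makes it support for either. McNemar's test also remains suitable for genuinely binary items, such as the Table 2 row for a breathlessness rating above 2.

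**What to change.** 1. In Comparisons, restrict McNemar's test to binary paired outcomes and state that the exact version is used.
2. For stopping reason, state whether the three rows are mutually exclusive. Pre-specify one binary outcome, stopped because of breathlessness (alone or with leg discomfort), tested by exact McNemar and reported as a paired risk difference with 95% CI.
3. Report the full three-category paired table (placebo by menthol) descriptively. If a test over all categories is wanted, name one exact marginal-homogeneity test in advance.
4. Correct the Table 2 caption to the paired tests in Comparisons: paired t-test, signed-rank and exact McNemar, in place of t-test, rank-sum and chi-square.

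The cost is a few lines of SAP text and one derived variable, with no new data and no change to the primary or co-primary analysis. The wording should be settled before the data are unblinded, so that the grouping is not chosen on the results.

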### Modeling:

Changes during CPET may be further analyzed using mixed-effects regression models to account for repeated measures.

### Reporting:

Estimates will be presented as mean differences (menthol minus placebo) with 95% confidence intervals (CIs). Statistical significance will be defined as two-sided  $p < 0.05$ .

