## Figures

Figures will be adapted from Abdallah et al. (2017) to illustrate perceptual and physiological responses during constant-load exercise testing. These will include:

- **Panels a–c:** Symptom ratings (breathlessness intensity, breathlessness unpleasantness, and leg discomfort) plotted against time during exercise for menthol and placebo conditions.
- **Panels d–f:** Post-dose differences (menthol minus placebo) at isotime and peak exercise for breathlessness intensity, unpleasantness, and exercise endurance time (EET), including individual participant data and group means with 95% CIs.
- **Panels g–i:** Distribution of individual responses and indication of clinically meaningful thresholds (e.g., minimally clinically important difference).

These figures will visualize symptom trajectories, treatment effects, and variability across participants, highlighting both statistical and clinical significance.

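### Non-normal exercise-test outcomes are tested by signed-rank but reported as a mean difference with 95% CI, so estimate and interval need not match the deciding test (minor)

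*SAP*

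**What the plan says.** **Test.** SAP, Comparisons: within-subject contrasts of menthol and placebo use the paired t-test for normal variables and "Wilcoxon signed-rank tests for non-normal variables". Breathlessness intensity at isotime (primary) and EET (co-primary) are both exercise-test outcomes, so both fall under this rule.

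**Decision.** SAP, Reporting: "Statistical significance will be defined as two-sided" p < 0.05.

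**Estimate.** SAP, Reporting: "Estimates will be presented as mean differences (menthol minus placebo) with 95% confidence intervals (CIs". No exception is made for variables sent to the rank test.

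**Table and figures.** Table 2 is headed "Parameter, mean (SD" and has only "Mean difference (95% CI" columns for the contrasts, although its caption names a rank procedure: "ranksum test for continuous non-normal variables and chi-square for categorical variables". Panels d–f in the Figures section show the differences "including individual participant data and group means with 95% CIs".

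**Description.** SAP, Data Presentation: "Skewed continuous variables will be expressed as median with range or interquartile range (IQR".

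**The concern.** The signed-rank test does not test the mean difference. It responds to the ranks of the differences, and the estimate that goes with it is the Hodges-Lehmann difference. A mean difference with a 95% CI answers another question and, for skewed or heavy-tailed differences, can answer it differently. In the rank-test branch the SAP therefore prints an estimate and interval that do not come from the test that decides the result.

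What is at stake is the coherence of the reported result. A reader of Table 2 could meet a co-primary outcome declared significant beside an interval that includes zero, and the plan names no matching interval to explain it.

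**Working it through.** **1. The sections side by side.** Comparisons offers two tests, chosen by normality. Reporting, Table 2 and panels d–f offer one kind of estimate, based on means. The two agree only in the paired-t branch. No section names a rank-based estimate or interval.

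**2. One simulated data set analysed as the SAP directs.** There is no figure in the SAP to reproduce, so the data are simulated: n = 20, EET differences in seconds, menthol minus placebo:

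−349, −82, −33, −19, −2, 1, 8, 22, 35, 44, 54, 62, 87, 106, 107, 115, 132, 197, 233, 284

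- Shapiro-Wilk p = 0.043, so the signed-rank test applies.
- The negative differences carry ranks 20 + 11 + 6 + 4 + 2 = 43 out of 20 × 21 / 2 = 210. Signed-rank p = 0.019: significant.
- Mean = 1002 / 20 = 50.1 s; SD = 130.8; SE = 130.8 / √20 = 29.24. The t-based 95% CI is 50.1 ± 2.093 × 29.24 = −11 to 111 s (t-test p = 0.103): includes zero.
- The result that matches the test is a Hodges-Lehmann difference of 54 s (95% CI 10 to 107): excludes zero.

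**3. How often this happens.** Every input is an assumption: n = 20 or 30, Shapiro-Wilk at 0.05 on the differences, t-based CI, log-normal EET with median 300 s, and three pairs of between-person/within-test log-SD. A conflict means that the rank branch is chosen and (signed-rank p < 0.05) disagrees with (CI excludes zero). There were 20,000 replicates per setting.

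| n | log-SDs | Rank branch used, +15% effect | Conflict, +15% effect | Conflict ÷ rank branch | Conflict, no effect |
|---|---|---|---|---|---|
| 20 | 0.3/0.2 | 15.8% | 1.98% | 12.5% | 0.46% |
| 20 | 0.4/0.2 | 24.4% | 3.24% | 13.3% | 0.80% |
| 20 | 0.6/0.25 | 43.0% | 6.22% | 14.5% | 1.50% |
| 30 | 0.3/0.2 | 20.7% | 2.56% | 12.4% | 0.66% |
| 30 | 0.4/0.2 | 32.2% | 4.61% | 14.3% | 1.17% |
| 30 | 0.6/0.25 | 58.4% | 9.78% | 16.7% | 2.10% |

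With the effect present, 64–80% of conflicts are of the kind p < 0.05 with a CI that includes zero.

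For Borg ratings (mean 4, between-person SD 1.5, within-test SD 1.0, effect 0.7 units, recorded in half or whole units) conflicts are about 0.6–1.6%.

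**4. Power for EET (%) under the same assumptions, +15% effect.** The current rule is the normality-dependent choice of test.

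| n | log-SDs | Current rule | Paired t | Signed-rank | Paired t on log EET |
|---|---|---|---|---|---|
| 20 | 0.3/0.2 | 52.0 | 51.2 | 51.2 | 55.5 |
| 20 | 0.4/0.2 | 51.2 | 49.6 | 50.9 | 55.5 |
| 20 | 0.6/0.25 | 33.2 | 29.5 | 33.7 | 38.9 |
| 30 | 0.3/0.2 | 71.4 | 70.7 | 71.1 | 74.4 |
| 30 | 0.4/0.2 | 69.6 | 67.7 | 69.9 | 74.4 |
| 30 | 0.6/0.25 | 47.8 | 42.8 | 48.7 | 55.3 |

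Against the current rule, the paired t-test loses 0.7 to 5.0 points and signed-rank changes by −0.8 to +0.9. The log-scale t-test, run separately with 5,000 replicates, exceeds signed-rank by 3.3 (74.4 − 71.1) to 6.6 (55.3 − 48.7) points. That gain depends on EET being log-normal.

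**The case against.** **What stands.** The problem is conditional. Nothing in the SAP says that the EET or Borg differences will be non-normal, and in five of the six settings above the paired-t branch is the more likely one. The upper rates need the widest spread assumed. Many conflicts are close calls: with the effect present, the larger of the two p-values is below 0.10 in roughly 55–70% of them. A signed-rank p-value beside a mean difference is also a common presentation that a careful reader can interpret.

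**What does not answer the point.** The medians in Data Presentation describe the variables; they supply neither a treatment-effect estimate nor its interval. The individual data and response distributions in the figures help a reader but do not provide one either. The protocol is not at hand and may fix the sample size, but that would not change a reporting rule that fails to fit the SAP's own test rule.

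**Stronger readings that a reader might infer.**
- *The result would be undecided.* It would not: Reporting makes the two-sided p-value the criterion.
- *False positives are inflated.* This is not shown. In the no-effect settings, with normality checked on the differences, rejection under the two-stage rule stays close to 5%.
- *Every result is affected.* The paired-t branch has no mismatch.
- *The rank-sum label in the Table 2 caption is part of this.* It differs from the signed-rank test in Comparisons, but that is a separate matter and nothing here rests on it.

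**Conclusion.** The point holds as a minor matter of reporting coherence. For any exercise-test outcome sent to the signed-rank test, including either primary outcome, the SAP prescribes an estimate and 95% CI that do not come from the deciding test and can fail to support its result.

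Under the stated assumptions a conflict would appear in about 2–10% of trials for EET with a 15% effect, 0.5–2% with none, and about 0.6–1.6% for Borg ratings with a 0.7-unit effect. These rates rest wholly on assumed sample size, spread, effect, normality rule and CI method, because the SAP states none of them. If normality were judged on the raw EET values instead of the differences, the rate with the effect would be 4.3–12.8%; the SAP does not say which is meant. A bootstrap interval for the mean would still target the mean and could still disagree with the test.

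**What to change.** In Comparisons and Reporting, name one analysis method in advance for each primary outcome, whatever a normality check shows, and take the estimate, 95% CI and p-value from it. Align Table 2 and panels d–f, and keep the other method as a sensitivity analysis.

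- **Borg ratings:** the paired t-test with the mean difference already fits Reporting. Its power is within 0.2 points of the current rule in the settings tried. A Hodges-Lehmann interval suits these ratings less well, because ties make it disagree with the signed-rank p-value more often: with whole-unit ratings, in 10.3% (n = 20) and 17.7% (n = 30) of the trials that fail the normality check, against 1.18% and 1.55% for the t-based interval.
- **EET:** the sponsor chooses one coherent option.
  1. Paired t-test with the mean difference. This keeps the stated estimate, at about 1–5 points of power.
  2. Signed-rank with the Hodges-Lehmann difference and matching CI, at about the same power as now. Analyse in seconds and treat the minutes in Table 2 as a display unit: the interval and test disagreed in 0.4–0.7% of simulated trials with whole seconds, but in 17–32% with whole minutes.
  3. Paired t-test on log EET, reported as a ratio with CI. This gives about 3–7 points more power than signed-rank if EET is log-normal.
- **Secondary variables:** for any tested by signed-rank, add the Hodges-Lehmann difference and CI beside the mean difference, or use the paired t-test throughout.

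The cost is wording only. Under the second or third EET option, the headline estimate is no longer a mean difference.
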